### **7.2.1 Definition of an Overdose for This Protocol and Reporting of Overdose to the Sponsor**

For purposes of this trial, an overdose will be defined as any dose exceeding the prescribed dose for MK-8628 by 1 dose in a 24 hour time period (i.e.  $\geq 3$  total doses in 24 hours). No specific information is available on the treatment of overdose of MK-8628. In the event of overdose, MK-8628 should be discontinued and the subject should be observed closely for signs of toxicity. Appropriate supportive treatment should be provided if clinically indicated.

If an adverse event(s) is associated with ("results from") the overdose of Sponsor's product or vaccine, the adverse event(s) is reported as a serious adverse event, even if no other seriousness criteria are met.

If a dose of Sponsor's product or vaccine meeting the protocol definition of overdose is taken without any associated clinical symptoms or abnormal laboratory results, the overdose is

reported as a non-serious Event of Clinical Interest (ECI), using the terminology “accidental or intentional overdose without adverse effect.”

All reports of overdose with and without an adverse event must be reported by the investigator within 24 hours to the Sponsor either by electronic media or paper. Electronic reporting procedures can be found in the EDC data entry guidelines. Paper reporting procedures can be found in the Investigator Trial File Binder (or equivalent).

### **7.2.2 Reporting of Pregnancy and Lactation to the Sponsor**

Although pregnancy and lactation are not considered adverse events, it is the responsibility of investigators or their designees to report any pregnancy or lactation in a subject (spontaneously reported to them), including the pregnancy of a male subject's female partner that occurs during the trial.

Pregnancies and lactations of subjects and female partners of male subjects from the time the consent form is signed but before treatment allocation/randomization must be reported by the investigator if they cause the subject to be excluded from the trial, or are the result of a protocol-specified intervention, including but not limited to washout or discontinuation of usual therapy, diet, placebo treatment or a procedure. Pregnancies and lactations of subjects and female partners of male subjects that occur from the time of treatment allocation/randomization through 30 days following cessation of Sponsor's product must be reported. All reported pregnancies must be followed to the completion/termination of the pregnancy. Pregnancy outcomes of spontaneous abortion, missed abortion, benign hydatidiform mole, blighted ovum, fetal death, intrauterine death, miscarriage and stillbirth must be reported as serious events (Important Medical Events). If the pregnancy continues to term, the outcome (health of infant) must also be reported.

Such events must be reported within 24 hours to the Sponsor either by electronic media or paper. Electronic reporting procedures can be found in the EDC data entry guidelines. Paper reporting procedures can be found in the Investigator Trial File Binder (or equivalent).

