Total bilirubin	$\leq 1.25$ X upper limit of normal (ULN) OR In case of liver involvement, $\leq 2$ x ULN will be allowed
Aspartate aminotransferase (AST) (SGOT) and alanine aminotransferase (ALT) (SGPT)	$< 3$ X ULN
Alkaline Phosphatase	If $> 2.5$ X ULN, then liver fraction should be $\leq 2.5$ X ULN
Chemistry	
Serum albumin	For NSCLC, CRPC and TNBC: $\geq 3.0$ g/dL
	For NMC: $\geq 2.0$ g/dL
Coagulation	
International Normalized Ratio (INR)	$\leq 1.5$

8. Have an interval of  $\geq 3$  weeks (or  $\geq 2$  weeks for NMC patients) since chemotherapy ( $\geq 6$  weeks for nitrosoureas or mitomycin C), immunotherapy, hormone therapy or any other anticancer therapy (including investigational) or surgical intervention resection, or  $\geq 3$  half-lives for monoclonal antibodies, or  $\geq 5$  half-lives for other non-cytotoxic agents (whichever is longer).

9. CRPC subjects must maintain ongoing androgen deprivation therapy with a gonadotropin releasing hormone (GnRH) analogue, antagonist or orchiectomy providing serum testosterone is < 50 ng/dL (<1.7 nmol/L).
10. Subjects receiving bisphosphonate or denosumab therapy must be on stable doses for at least 4 weeks before initiating study treatment
11. Female subjects of childbearing potential must have a negative urine or serum pregnancy test within 72 hours prior to receiving the first dose of study medication. If the urine test is positive or cannot be confirmed as negative, a serum pregnancy test will be required.
12. Female subjects of childbearing potential should be willing to use an adequate method of contraception as outlined in section 5.7.3– Contraception, for the course of the study through 90 days after the last dose of study medication. Note: Abstinence is acceptable if this is the usual lifestyle and preferred contraception for the subject.
13. Male subjects of childbearing potential must agree to use an adequate method of contraception as outlined in Section 5.7.3 – Contraception, starting with the first dose of trial treatment through 90 days after the last dose of study medication. Note: Abstinence is acceptable if this is the usual lifestyle and preferred contraception for the subject.

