### **5.7.3 Contraception**

MK-8628 may have adverse effects on a fetus in utero. Furthermore, it is not known if MK-8628 has transient adverse effects on the composition of sperm.

For this trial, male subjects will be considered to be of non-reproductive potential if they have azoospermia (whether due to having had a vasectomy or due to an underlying medical condition).

Female subjects will be considered of non-reproductive potential if they are either:

- (1) postmenopausal (defined as at least 12 months with no menses without an alternative medical cause; in women <45 years of age a high follicle-stimulating hormone (FSH) level in the postmenopausal range may be used to confirm a post-menopausal state in women not using hormonal contraception or hormonal replacement therapy. In the absence of 12 months of amenorrhea, a single FSH measurement is insufficient.);

OR

- (2) have had a hysterectomy and/or bilateral oophorectomy, bilateral salpingectomy, or bilateral tubal ligation/occlusion at least 6 weeks prior to screening;

OR

- (3) has a congenital or acquired condition that prevents childbearing.

Female and male subjects of reproductive potential must agree to avoid becoming pregnant or impregnating a partner, respectively, while receiving study drug MK-8628 and for 90 days after the last dose of study drug. Subjects must comply with one of the following:

(1) practice abstinence† from heterosexual activity;

OR

(2) use (or have their partner use) acceptable contraception during heterosexual activity.

Acceptable methods of contraception are‡:

Single method (one of the following is acceptable):

- intrauterine device (IUD)
- vasectomy of a female subject's sole male partner
- contraceptive rod implanted into the skin

Combination method (requires use of two of the following):

- diaphragm with spermicide (cannot be used in conjunction with cervical cap/spermicide)
- cervical cap with spermicide (nulliparous women only)
- contraceptive sponge (nulliparous women only)
- male condom or female condom (cannot be used together)
- hormonal contraceptive: oral contraceptive pill (estrogen/progestin pill or progestin-only pill), contraceptive skin patch, vaginal contraceptive ring, or subcutaneous contraceptive injection

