†Abstinence (relative to heterosexual activity) can be used as the sole method of contraception if it is consistently employed as the subject's preferred and usual lifestyle and if considered acceptable by local regulatory agencies and ERCs/IRBs. Periodic abstinence (e.g., calendar, ovulation, sympto-thermal, post-ovulation methods, etc.) and withdrawal are not acceptable methods of contraception.

‡If a contraceptive method listed above is restricted by local regulations/guidelines, then it does not qualify as an acceptable method of contraception for subjects participating at sites in this country/region.

Subjects should be informed that taking the study medication may involve unknown risks to the fetus (unborn baby) if pregnancy were to occur during the study. In order to participate in the study, subjects of childbearing potential must adhere to the contraception requirement (described above) from the day of study medication initiation (or 14 days prior to the initiation of study treatment [Day 1] for oral contraception) throughout the study period up to 90 days after the last dose of trial therapy. If there is any question that a subject of childbearing potential will not reliably comply with the requirements for contraception, that subject should not be entered into the study.

Monthly pregnancy testing is recommended per local standards if applicable.

**For countries (e.g., Sweden and Norway) or sites that follow the Clinical Trial Facilitation Group (CTFG) guidance, please use the following:**

MK-8628 may have adverse effects on a fetus in utero. Furthermore, it is not known if it may have transient adverse effects on the composition of sperm. Therefore, non-pregnant, non-breastfeeding women may only be enrolled if they are willing to follow the CTFG Guidance (Final Version 2014-09-15, Sections 4.1 and 4.2) for highly effective birth control as outlined below, or are considered to be highly unlikely to conceive. Highly unlikely to conceive is defined as 1) surgically sterilized, or 2) postmenopausal (a woman who is  $\geq 45$  years of age and has not had menses for greater than 1 year will be considered postmenopausal), or 3) not heterosexually active for the duration of the study. Subjects should use birth control methods that can achieve a failure rate of less than 1% per year when used consistently and correctly and are considered as highly effective birth control methods. Such methods include:

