- Combined (estrogen and progestogen containing) hormonal contraception associated with inhibition of ovulation:
  - o Oral
  - o Intravaginal
  - o Transdermal
- Progestogen-only hormonal contraception associated with inhibition of ovulation:
  - o Oral
  - o Injectable
  - o Implantable
- Intrauterine device (IUD)
- Intrauterine hormone-releasing system (IUS)
- Bilateral tubal occlusion
- Vasectomised partner
- Sexual abstinence

Subjects should start using birth control from study Visit 1 throughout the study period up to 90 days after the last dose of study therapy.

Subjects should be informed that taking the study medication may involve unknown risks to the fetus (unborn baby) if pregnancy were to occur during the study. In order to participate in the study they must adhere to the contraception requirement (described above) for the duration of the study and during the follow-up period defined in Section 7.2.2 – Reporting of Pregnancy and Lactation to the Sponsor. If there is any question that a subject will not reliably comply with the requirements for contraception, that subject should not be entered into the study.

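### The explicit pregnancy-reporting window closes 30 days after treatment, while the protocol requires contraception for 90 days, leaving days 31–90 to general or outcome-based reporting routes

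*Combined protocol and SAP*

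**What the plan says.** **Reporting window.** Section 7.2.2 requires reporting of pregnancies and lactations of subjects and of male subjects' female partners "that occur from the time of treatment allocation/randomization through 30 days following cessation of" the sponsor's product. Pregnancies so reported must be followed to their end, and listed adverse outcomes are reported as serious events.

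**Contraception period.** Section 5.1.2 requires it of female subjects "for the course of the study through 90 days after the last dose of study medication" (criterion 12) and of male subjects "starting with the first dose of trial treatment through 90 days after the last dose of study medication" (criterion 13). Section 5.7.3 requires both sexes to avoid pregnancy "while receiving study drug MK-8628 and for 90 days after the last dose of study drug", and its general text repeats the requirement "throughout the study period up to 90 days after the last dose of trial therapy". The stated reason is: "MK-8628 may have adverse effects on a fetus in utero. Furthermore, it is not known if MK-8628 has transient adverse effects" on sperm.

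**CTFG text.** The alternative wording in 5.7.3 for countries or sites that follow the CTFG guidance also gives 90 days. It then asks for adherence "for the duration of the study and during the follow-up period defined in Section 7.2.2". The only post-treatment period in 7.2.2 is 30 days.

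**Contact after treatment.** Section 7.1.5.4 schedules the safety visit 30 days (+5) after the last intake. Later visits are six-weekly disease assessments for subjects who stopped without progression. The flow chart in Section 6.0 lists a pregnancy test at screening only; Section 5.7.3 recommends monthly testing where local standards call for it.

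**The concern.** The protocol asks subjects to avoid conception for three months after the last dose and ties this to possible harm to a fetus and unknown effects on sperm. Its explicit instruction to sites to report a pregnancy stops after one month. A conception on day 60, for example, breaches the contraception requirement for a stated safety reason, yet falls outside the dated reporting rule.

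Follow-up to completion under 7.2.2 applies to pregnancies that have been reported. A pregnancy outside the window has no clear trigger for that follow-up. What is at stake is prospective information on pregnancies begun soon after exposure, in a trial that admits NMC subjects from age 16, women with TNBC and men whose partners may conceive.

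The CTFG cross-reference adds a second difficulty: a site that looks up the period it names finds 30 days, not 90.

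**Working it through.** The plan gives no figure of its own on this point, so there is none to reproduce. I take the last dose and cessation of product as the same date.

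**Inputs**
- Post-treatment contraception period: 90 days (Sections 5.1.2 and 5.7.3).
- Post-treatment pregnancy-reporting window: 30 days (Section 7.2.2).
- Last safety visit scheduled for all subjects: day 30, at latest day 35 (Section 7.1.5.4).

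**Step 1: share of contraception days outside the window**
- 90 − 30 = 60 days; 60/90 = 66.7%.

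**Step 2: share remaining after the last safety visit, if that visit falls on day 35**
- 90 − 35 = 55 days; 55/90 = 61.1%.

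**Step 3: sensitivity to the denominator.** The two-thirds refers to the post-treatment period only. Against treatment plus 90 days the share is smaller. The documents give no expected treatment duration, so the number of 21-day cycles is an assumption:

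| Assumed cycles | Days on treatment + 90 | 60 days as share |
|---|---|---|
| 1 | 111 | 54.1% |
| 2 | 132 | 45.5% |
| 4 | 174 | 34.5% |
| 8 | 258 | 23.3% |

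**Step 4: does another passage cover days 31–90?**
- *Opening of 7.2.2.* It sets a general duty to report pregnancies that come to the site unprompted, including a partner's pregnancy during the trial. It has no day count. Section 5.10 ends the trial at the last subject's last contact, so the sentence can be read to reach past day 30 for many subjects. For the last subjects it may not. It is also passive, and the dated 30-day rule follows it.
- *Section 5.7.4.* For a female subject it addresses pregnancy while on treatment. The sentence on partners has no day limit but refers back to 7.2.2.
- *Drug-related events.* Section 7.2.3.1 keeps serious events judged related reportable at any time, and footnote g of the flow chart does the same for any drug-related adverse event after 30 days. Section 7.2.2 says that pregnancy itself is not an adverse event, so these routes start from an adverse outcome and a causality judgement.
- *Disease-assessment visits.* These give contact after day 30 only for subjects who stopped without progression, and no pregnancy test or enquiry is listed for them.

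No passage sets a pregnancy-reporting duty to day 90.

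**Step 5: after the change.** With a window equal to the contraception period, 90 − 90 = 0 days remain outside.

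**The case against.** The strongest reply is that the 30 days is deliberate. It matches the adverse-event and serious-event windows in Sections 7.2 and 7.2.3.1. Section 4.2.2.1 gives a half-life of about 5–6 hours, so 30 days (720 hours) is at least 720/6 = 120 half-lives. A contraception margin may reasonably be longer than a reporting window. This is possible, but the documents offer no such reasoning. The 90 days stands next to the stated fetal and sperm concerns, and the half-life does not settle an effect on sperm that the protocol calls unknown.

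Four stronger readings are tempting, and the documents do not support them:

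- A reader might infer that pregnancies begun on days 31–90 are lost, or need not be reported at all. The routes in Step 4 make that too strong. They are partial, but drug-related serious outcomes remain reportable, and Table 12 counts a congenital anomaly whenever it is diagnosed.
- A reader might infer that the protocol declares a 90-day at-risk period. It sets a contraception period; reading that as the period of risk is an inference from the stated reason.
- A reader might take 67% as the share of exposed pregnancies missed. It is a share of calendar days and weights day 31 and day 89 equally. The documents give no pregnancy rate. With at most about 72 subjects, all with advanced cancer and some with CRPC, the number is likely to be small.
- A reader might call the CTFG text a flat contradiction. Following 90 days satisfies both sentences, and the second refers back to the requirement already described. It is an ambiguous cross-reference.

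**Conclusion.** The mismatch stands. The explicit window in 7.2.2 covers 30 of the 90 post-treatment contraception days and leaves 60 (67%) to routes that are general, refer back to 7.2.2, or begin only with a drug-related event. The last safety visit scheduled for all subjects falls at or just after the point where the window closes. The CTFG cross-reference makes the end date harder to read at the sites that use it.

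The conclusion rests on the two stated periods and on the absence of any dated duty beyond 30 days. It does not depend on how many pregnancies would occur, which the documents do not allow one to estimate. The point should be corrected for safety surveillance and internal consistency. It leaves the cycle 1 DLT endpoint, the sample size and the RP2D decision untouched.

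**What to change.** - Reconcile Section 7.2.2 with Sections 5.1.2, 5.7.3 and 5.7.4 so that pregnancy reporting and follow-up, for subjects and partners, cover the full post-treatment contraception period the protocol already states. If the shorter window is intended, state the reason and say how a pregnancy conceived between the two dates is handled.
- State in 5.7.4 that its partner sentence follows the same window.
- Correct the CTFG cross-reference in 5.7.3 so that the contraception period is stated once and no longer depends on 7.2.2.

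The cost is an amendment to wording and a few additional reports after day 30. The change adds no visit, so ascertainment after the safety visit would still depend largely on subjects telling the site. It would, however, make clear to the site what to do when they do.

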### **7.2.3 Immediate Reporting of Adverse Events to the Sponsor**

#### **7.2.3.1 Serious Adverse Events**

A serious adverse event is any adverse event occurring at any dose or during any use of Sponsor's product that:

- Results in death;
- Is life threatening;
- Results in persistent or significant disability/incapacity;
- Results in or prolongs an existing inpatient hospitalization;
- Is a congenital anomaly/birth defect;
- Is an other important medical event.

**Note:** In addition to the above criteria, adverse events meeting either of the below criteria, although not serious per ICH definition, are reportable to the Sponsor in the same timeframe as SAEs to meet certain local requirements. Therefore, these events are considered serious by the Sponsor for collection purposes.

- Is a new cancer (that is not a condition of the study);
- Is associated with an overdose.

Refer to [Table 12](#) for additional details regarding each of the above criteria.

For the time period beginning when the consent form is signed until treatment allocation/randomization, any serious adverse event, or follow up to a serious adverse event, including death due to any cause, other than progression of the cancer under study (reference Section 7.2.3.3 for additional details), that occurs to any subject must be reported within 24 hours to the Sponsor if it causes the subject to be excluded from the trial, or is the result of a protocol-specified intervention, including but not limited to washout or discontinuation of usual therapy, diet, placebo treatment or a procedure.

For the time period beginning at treatment allocation/randomization through 30 days following cessation of treatment, any serious adverse event, or follow up to a serious adverse event, including death due to any cause other than progression of the cancer under study (reference Section 7.2.3.3 for additional details), whether or not related to the Sponsor's product, must be reported within 24 hours to the Sponsor either by electronic media or paper. Electronic reporting procedures can be found in the EDC data entry guidelines. Paper reporting procedures can be found in the Investigator Trial File Binder (or equivalent).

Additionally, any serious adverse event, considered by an investigator who is a qualified physician to be related to the Sponsor's product that is brought to the attention of the investigator at any time following consent through the end of the specified safety follow-up period specified in the paragraph above, or at any time outside of the time period specified in the previous paragraph also must be reported immediately to the Sponsor.

All subjects with serious adverse events must be followed up for outcome.

### **7.2.3.2 Events of Clinical Interest**

Selected non-serious and serious adverse events are also known as Events of Clinical Interest (ECI) and must be reported to the Sponsor.

For the time period beginning when the consent form is signed until treatment allocation/randomization, any ECI, or follow up to an ECI, that occurs to any subject must be reported within 24 hours to the Sponsor if it causes the subject to be excluded from the trial, or is the result of a protocol-specified intervention, including but not limited to washout or discontinuation of usual therapy, diet, placebo treatment or a procedure.

For the time period beginning at treatment allocation/randomization through 30 days following cessation of treatment, any ECI, or follow up to an ECI, whether or not related to the Sponsor's product, must be reported within 24 hours to the Sponsor, either by electronic media or paper. Electronic reporting procedures can be found in the EDC data entry guidelines. Paper reporting procedures can be found in the Investigator Trial File Binder (or equivalent).

Events of clinical interest for this trial include:

1. an overdose of Sponsor's product, as defined in Section 7.2.1 - Definition of an Overdose for This Protocol and Reporting of Overdose to the Sponsor, that is not associated with clinical symptoms or abnormal laboratory results.
2. an elevated AST or ALT lab value that is greater than or equal to 3X the upper limit of normal and an elevated total bilirubin lab value that is greater than or equal to 2X the upper limit of normal and, at the same time, an alkaline phosphatase lab value that is less than 2X the upper limit of normal, as determined by way of protocol-specified laboratory testing or unscheduled laboratory testing.\*

\*Note: These criteria are based upon available regulatory guidance documents. The purpose of the criteria is to specify a threshold of abnormal hepatic tests that may require an additional evaluation for an underlying etiology. The trial site guidance for assessment and follow up of these criteria can be found in the Investigator Trial File Binder (or equivalent).

3. an elevated total bilirubin lab value that is greater than or equal to 2X the upper limit of normal.
4. an elevated AST or ALT lab value that is greater than or equal to 5X the upper limit of normal.

\*Note: For further guidance on the monitoring, treatment and follow-up of any ECI related to potential drug-induced liver injury (DILI), please see Section 12.7.

5. For the purpose of this dose-finding study, any suspected DLT occurring during dose escalation will be considered as medically important and reported as an ECI. If the event also meets the criteria for seriousness, follow the reporting guidelines for Serious Adverse Events (SAEs) outlined in Section 7.2.3.1.

